5.5 SAMPLE STORAGE, TRACKING AND DISPOSITION

Samples will be ordered in CRIS and tracked through the Clinical Trial Data Management system. Should a CRIS screen not be available, the CRIS downtime procedures will be followed. Samples will not be sent outside NIH without appropriate approvals and/or agreements, if required.

5.5.1 Procedures for Storage of Specimens in the NOB

Patient samples, collected for the purpose of research under IRB approved protocols conducted by NOB, may be archived in the NOB laboratory. All data associated with archived clinical research samples is entered into the NCI Labmatrix database. These databases are stored on the NCI group drive in the Clinical Service folder. Access to this folder is limited to NOB research staff, requiring individual login and password..

The data recorded for each sample includes the patient ID, trial name/protocol number, date drawn/collected, treatment cycle/post-transplant time point, cell source (e.g. peripheral blood, marrow, tissue) as well as box and freezer location. Patient demographics that correlate treatment outcomes and therapies with the samples can be obtained only through the NCI clinical records. All received samples will receive a unique bar code number, which will be added to the sample NCI Labmatrix database. Only this bar code will be recorded on the sample vial and the vials will not be traceable back to patients without authorized access to the NCI Labmatrix database.

Samples are stored in freezers at -80⁰C (sera, plasma, tissue samples) or under liquid nitrogen (cells), according to stability requirements. These freezers are located onsite at the NOB laboratory. Access to samples from a protocol for research purposes will be by permission of the Principal Investigator.

5.5.2 Procedures for Storage of Tissue Specimens in the Laboratory of Pathology

Tissues designated for clinical diagnostics are transported to the Laboratory of Pathology (LP) where they are examined grossly, and relevant portions are fixed, embedded in paraffin and sectioned and stained for diagnostic interpretation. Unutilized excess tissues are stored for up to three months, in accordance with College of American Pathologists/Joint Commission on Accreditation of Healthcare Organizations (CAP/JCAHO) guidelines, and then discarded. Following completion of the diagnostic workup, the slides and tissue blocks are stored indefinitely in the LP's clinical archives. All specimens are catalogued and retrieved utilizing the clinical laboratory information systems, in accordance with CAP/JCAHO regulations. The use of any stored specimens for research purposes is only allowed when the appropriate IRB approval has been obtained. In some cases, this approval has been obtained via the original protocol on which the patient was enrolled.

5.5.3 Procedures for Storage of Specimens in the Genetic Branch under Supervision of [name]

Patient samples, collected for the purpose of research under IRB approved protocols conducted by CGB, may be archived in the CGB laboratory. All data associated with archived clinical research samples is entered into the NCI Labmatrix database. These databases are stored on the NCI group drive in the Clinical Service folder. Access to this folder is limited to CGB research staff, requiring individual login and password. .

The data recorded for each sample includes the patient ID, trial name/protocol number, date drawn/collected, treatment cycle/post-transplant time point, cell source (e.g. peripheral blood, marrow, tissue) as well as box and freezer location. Patient demographics that correlate treatment outcomes and therapies with the samples can be obtained only through the NCI clinical records. All received samples will receive a unique bar code number, which will be added to the sample NCI Labmatrix database. Only this bar code will be recorded on the sample vial and the vials will not be traceable back to patients without authorized access to the NCI Labmatrix database.

Samples are stored in freezers at -80° C (sera, plasma, tissue samples) or under liquid nitrogen (cells), according to stability requirements. These freezers are located onsite at the CGB laboratory. Access to samples from a protocol for research purposes will be by permission of the Principal Investigator.

5.5.4 Procedures for Storage of Specimens for Laboratory of [name]

Samples will be processed immediately by the [name] laboratory. Biospecimens will be collected and processed using validated SOPs that will ensure both specimen quality and patient confidentiality. Using a computerized inventory system and a backup hardcopy process, all specimen collection and processing steps will be documented and the specific location of each specimen will be tracked. Each new specimen collected will be assigned a unique barcode identifier that can be linked to the original specimen collected and other relevant information within the inventory system. Specimen labels will indicate protocol number, order in which the patient enrolled on the trial, type of sample, collection time, and total volume collected, as appropriate. The inventory process contains other security provisions sufficient to safeguard patient privacy and confidentiality. Access to the inventory system and associated documents will be restricted to appropriate individuals. Requests to use specimens stored in the repository must be approved. SOPs ensure that any changes in informed consent made by a patient and relayed to the PI will be reflected in the inventory system to ensure that specimens are destroyed as appropriate. All laboratory personnel will be trained to adhere to SOPs and will be monitored for high-quality performance.

5.5.5 Protocol Completion/Sample Destruction

All specimens obtained in the protocol are used as defined in the protocol. Any tumor tissue blocks or FFPE specimens that are remaining at the completion of the protocol will be stored at the Laboratory of Pathology. The study will remain open so long as sample or data analysis continues. Samples from consenting subjects will be stored until they are no longer of scientific value or if a subject withdraws consent for their continued use, at which time they will be destroyed.

If the patient withdraws consent the participants' data will be excluded from future distributions, but data that have already been distributed for approved research use will not be able to be retrieved.

The PI will record any loss or unanticipated destruction of samples as a deviation. Reporting will be per the requirements of section [7.2](#).

5.6 SAMPLES FOR GENETIC/GENOMIC ANALYSIS

5.6.1 Description of The Scope of Genetic/Genomic Analysis

Tumor and blood or saliva specimens will be collected, and genomic analyses will be performed. Tumor genetic material will undergo evaluation for whole exome sequencing and RNA sequencing

evaluating for possible neoantigens and to provide the immunologic microenvironmental landscape respectively. Genetic material containing germline DNA, including blood or saliva will be obtained for whole exome sequencing, which will be performed to combine with WES data from tumor tissue to identify tumor specific somatic mutations and neoantigens.

The genomic tests to determine the mutation burden are going to be performed by CLIA laboratories including Laboratory of Pathology and Genetic Branch. Formalin fixed, and paraffin embedded (FFPE) tumor tissue will be used for genomic material extraction. The whole exome sequencing will be performed to generate the tumor mutation burden from the non-synonymous mutations. Tumor genomic analysis will not be repeated if already performed on another NIH protocol.

5.6.2 Management of Results

Subjects will be contacted if a clinically actionable gene variant is discovered. For the purpose of this study, clinically actionable findings are defined as disorders appearing in the American College of Medical Genetics and Genomics recommendations for the return of incidental findings that is current at the time of primary analysis. (A list of current guidelines is maintained on the CCR intranet: <https://ccrod.cancer.gov/confluence/display/CCRCRO/Incidental+Findings+Lists>. Subjects will be contacted at that time with a request to provide a blood sample to be sent to a CLIA certified laboratory.

5.6.3 A Certificate of Confidentiality will be obtained for the study as described in section 13.4

5.6.4 Genetic Counseling

If the research findings are verified in the CLIA certified lab, the subject will be offered the opportunity to come to NIH (at our expense) to have genetic education and counseling with the NCI Genetics Branch to explain this result. If the subject does not want to come to NIH, a referral to a local genetic healthcare provider will be provided (at their expense). This is the only time during the course of the study that incidental findings will be returned. No interrogations regarding clinically actionable findings will be made after the primary analysis.

6 DATA COLLECTION AND EVALUATION

6.1 DATA COLLECTION

The PI will be responsible for overseeing entry of data into a 21 CFR Part 11-compliant data capture system provided by the NCI CCR and ensuring data accuracy, consistency and timeliness. The principal investigator, associate investigators/research nurses and/or a contracted data manager will assist with the data management efforts. Primary and final analyzed data will have identifiers so that research data can be attributed to an individual human subject participant.

All adverse events, including clinically significant abnormal findings on laboratory evaluations, regardless of severity, will be followed until return to baseline or stabilization of event. Document AEs from the first study intervention, Day 1 through 100 days after the study intervention was last administered. Beyond 100 days after the last intervention, only adverse events which are serious and related to the study intervention need to be recorded.

An abnormal laboratory value will be recorded in the database as an AE only if the laboratory abnormality is characterized by any of the following:

- Results in discontinuation from the study
- Is associated with clinical signs or symptoms
- Requires treatment or any other therapeutic intervention
- Is associated with death or another serious adverse event, including hospitalization.
- Is judged by the Investigator to be of significant clinical impact

If any abnormal laboratory result is considered clinically significant, the investigator will provide details about the action taken with respect to the test drug and about the patient's outcome.

Grade 1 AEs will not be collected.

All deaths will be recorded.

End of study procedures: Data will be stored according to HHS, FDA regulations, and NIH Intramural Records Retention Schedule as applicable.

Loss or destruction of data: Should we become aware that a major breach in our plan to protect subject confidentiality and trial data has occurred, this will be reported expeditiously per requirements in section [7.2.1](#)

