Grade 2	Hold until \leq Grade 1 or baseline. Consider steroid treatment if persists $> 5-7$ days.
Grade 3	Off protocol therapy.
Grade 4	Off protocol therapy.
Patients with grade 2 symptoms but normal colonoscopy and biopsies may be retreated after resolution.	
Patients with grade 2 persistent symptoms greater than 14 days who require steroids should be taken off study treatment.	
Please evaluate pituitary function prior to starting steroids if possible without compromising acute care.	
Evaluation for all patients for additional causes includes C. diff , acute and self-limited infectious and foodborne illness, ischemic bowel, diverticulitis, and IBD.	
Recommended management: see GI AE management Algorithm (Appendix C).	

Pancreatitis Amylase/Lipase	Management
Grade 1	Continue treatment if asymptomatic.
Grade 2	Hold until \leq Grade 1. Resume at same dose level if asymptomatic. Asymptomatic Grade 2 is defined as elevation of both amylase and lipase.

Pancreatitis Amylase/Lipase	Management
Grade 3	Off protocol therapy
Grade 4	Off protocol therapy

Patients may develop symptomatic and radiologic evidence of pancreatitis as well as DM and DKA. Lipase and/or amylase elevation may occur during the period of steroid withdrawal and with other immune mediated events or associated with colitis, hepatitis, and patients who have asymptomatic lipase and/or amylase elevation typically have self-limited course and may be retreated.
 
For treatment management of symptomatic pancreatitis please follow the Hepatic Adverse Event Management Algorithm (Appendix C).
	

Pneumonitis	Management
Grade 1	Hold dose pending evaluation and resolution to baseline including baseline pO ₂ . Resume; no change in dose after pulmonary and/or ID consultation
Grade 2	Hold dose pending evaluation and resolution to baseline including baseline pO ₂ . Resume; no change in dose after pulmonary and/or ID consultation if lymphocytic pneumonitis is excluded. Off study if grade 2 symptoms do not improve or worsen after 2 weeks of steroids and dose delay.
Grade 3	Off protocol therapy.
Grade 4	Off protocol therapy.

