
Distinguishing inflammatory pneumonitis is often a diagnosis of exclusion for patients who do not respond to antibiotics and have no causal organism identified including influenza. Most patients with respiratory failure or hypoxia will be treated with steroids. Bronchoscopy may be required and analysis of lavage fluid for lymphocytic predominance may be helpful. Patients with new lung nodules should be evaluated for sarcoid like granuloma. Please consider recommending seasonal influenza killed vaccine for all patients.
 
Recommended management: See Pulmonary Adverse Event Management Algorithm (Appendix C).
	

Other GI Nausea - Vomiting	Management
Grade 1	No change in dose.
Grade 2	Hold pending evaluation for gastritis duodenitis and other immune adverse events or other causes. Resume at same dose level after resolution to \leq Grade 1.
Grade 3	Hold pending evaluation until \leq Grade 1. Resume at same dose level. If symptoms do not resolve within 7 days with symptomatic treatment patients should go off protocol therapy
Grade 4	Off protocol therapy.

Other GI Nausea - Vomiting	Management
Patients with grade 2 or 3 N-V should be evaluated for upper GI inflammation and other immune related events.	

Fatigue	Management
Grade 1	No change in dose.
Grade 2	No change in dose
Grade 3	Hold until \leq Grade 2. Resume at same dose level
Fatigue is the most common adverse event associated with immune checkpoint therapy. Grade 2 or greater fatigue should be evaluated for associated or underlying organ involvement including pituitary, thyroid, and hepatic, or muscle (CPK) inflammation	

Neurologic events	Management
Grade 1	Hold dose pending evaluation and observation. Resume with no change in dose.
Grade 2	Hold dose pending evaluation and observation. Hold until \leq Grade 1.* Off protocol therapy if treatment with steroids is required. Resume at same dose level for peripheral isolated n. VII (Bell's palsy)
Grade 3	Off protocol therapy
Grade 4	Off protocol therapy
*Patients with any CNS events including aseptic meningitis, encephalitis, or myopathy, peripheral demyelinating neuropathy, cranial neuropathy (other than peripheral n. VII), GB syndrome, myasthenia gravis should be off protocol therapy.	
Recommended management: See Neurologic Adverse Event Management Algorithm (Appendix C)	

Endocrine Hypophysitis Adrenal Insufficiency	Management

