8.5 SAFETY REPORTING CRITERIA TO THE PHARMACEUTICAL COLLABORATOR (BRISTOL MYERS SQUIBB)

8.5.1 Non-Serious Adverse Event Collection and Reporting

The study team will send:

Non-serious Adverse Events are to be provided to BMS in aggregate via interim or final study reports as specified in the agreement or, if a regulatory requirement [e.g. IND US trial] as part of an annual reporting requirement.

The collection of non-serious AE information should begin at initiation of study drug. All non-serious adverse events (not only those deemed to be treatment-related) should be collected continuously during the treatment period and for a minimum of 100 days following the last dose of study treatment.

Non-serious AEs should be followed to resolution or stabilization or reported as SAEs if they become serious. Follow-up is also required for non-serious AEs that cause interruption or discontinuation of study drug and for those present at the end of study treatment as appropriate.

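### Section 6.1 bars collection of Grade 1 adverse events while 8.5.1 sets no grade limit, so non-serious Grade 1 events that hold drug under 3.3 would be missing from the AE dataset and the safety tables

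*Combined protocol and SAP*

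**What the plan says.** Section 6.1 (Data Collection) contains three relevant instructions. On follow-up: "All adverse events, including clinically significant abnormal findings on laboratory evaluations, regardless of severity, will be followed until return to baseline" or stabilization. On the window: "Document AEs from the first study intervention, Day 1 through 100 days after the study intervention was last administered". Then, after the criteria for recording laboratory abnormalities: "Grade 1 AEs will not be collected". That last sentence has no exception for serious, immune-related or dose-hold events.

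Section 8.5.1, on reporting to the drug supplier, says: "All non-serious adverse events (not only those deemed to be treatment-related) should be collected continuously during the treatment period" and for at least 100 days after the last dose. It adds that non-serious events causing interruption or discontinuation of study drug must be followed up. It names no grade.

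Section 3.3 (Dose Modifications) holds drug at Grade 1 in two tables. For Grade 1 pneumonitis: "Hold dose pending evaluation and resolution to baseline", with pulmonary and/or infectious-disease consultation before resuming. For Grade 1 neurologic events: "Hold dose pending evaluation and observation. Resume with no change in dose".

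Section 10.3.3 plans frequency tables of AEs by type and grade. Section 10.2.1 makes every patient evaluable for toxicity from the first treatment. Neither mentions that Grade 1 is left out.

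**The concern.** Sections 6.1 and 8.5.1 give opposite instructions on the same act for the same events. If sites follow 6.1, some of the missing events are not trivial: they are early lung or neurologic events that led the investigator to withhold drug. In a brain-tumour population on a checkpoint inhibitor, a safety summary should show these.

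What is at stake is the completeness of the safety data and how they will be read. A table by type and grade that holds only Grade 2 and above, but does not say so, invites the reader to treat the absence of Grade 1 as an observation. Aggregate reports to the supplier drawn from the same dataset would carry the same gap. The exploratory analyses in 10.3.5, which relate immune changes to treatment-related toxicity, could be affected too if toxicity is taken from the AE dataset, because a patient whose only related event was Grade 1 would be counted as having none. The documents do not define that toxicity variable, so this last point is conditional.

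**Working it through.** No arithmetic applies. The check sets the sections against each other by type of event.

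**1. Section 6.1 against 8.5.1.** Both sections speak of events being collected. The windows agree: 6.1 runs from Day 1 to 100 days after the last administration, and 8.5.1 covers treatment plus at least 100 days. Only the treatment of grade differs.

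| Event | Section 6.1 | Other sections |
|---|---|---|
| Non-serious, Grade 2 or above | Collected | Collected (8.5.1) |
| Non-serious, Grade 1 | Not collected | Collected (8.5.1) |
| Serious, Grade 1 | Not collected, if read literally | Recorded and reported as an SAE (8.2, 8.3, 8.5.2) |

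The direct, unresolved conflict is the middle row. In the last row the SAE sections supply the record, because seriousness (8.1.2) is defined separately from CTCAE grade (8.1.4).

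**2. Can another section resolve it?** Section 8.2 asks that AEs in the collection period be documented whatever their relationship to drug. It sets no grade limit and refers to 6.1 for the timeframe only. The laboratory criteria in 6.1 decide which laboratory abnormalities count as AEs; they do not explain a general Grade 1 exclusion. Neither resolves the conflict.

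**3. Which Grade 1 events change treatment?** The Grade 1 rows of the tables in 3.3 were read in turn.
- Pneumonitis and neurologic events: drug is held.
- Skin, liver, renal, nausea and vomiting, fatigue, fever and the two tables for all other events: treatment continues or dose is unchanged.
- Diarrhea/colitis: continuing is at the investigator's discretion. Pancreatitis: continuing is conditional on no symptoms. Endocrine: treatment may continue during evaluation.

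So two tables hold drug outright at Grade 1. Section 3.3 also stops treatment for an AE unresolved for 4 weeks and does not limit that rule by grade.

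**4. One event traced through the plan.** Take a non-serious Grade 1 pneumonitis.
- Section 3.3: dose held.
- Section 6.1: no AE entry.
- Section 8.5.1: collected, and followed up because it interrupted drug.
- Section 10.3.3: absent from the tables if 6.1 is followed, with nothing to tell the reader.

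A non-serious Grade 1 neurologic event takes the same path.

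**5. Size.** The documents give no Grade 1 rate for any of these events, so no count or percentage of patients can be derived.

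**The case against.** The case on the other side has real content.

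- *Restricting collection to Grade 2 and above can be a deliberate economy.* True, but the plan gives no rationale, and 8.5.1 and 10.3.3 do not reflect such a choice.
- *Section 6.1 does not plainly contradict itself.* A reader might infer that it does, because AEs are followed "regardless of severity, will be followed until return to baseline or stabilization of event" and Grade 1 is then dropped. But follow-up can mean clinical follow-up without a database entry. The internal tension is therefore weak; the conflict with 8.5.1 carries the point.
- *No breach of obligations to the supplier is shown.* A reader might infer one. Section 8.5.1 says events should be collected and ties aggregate reporting to the agreement or to annual regulatory reporting. The agreement is not among the documents, so only a conflict between sections can be shown.
- *Dose holds need not go unexplained.* A reader might infer that they would have no recorded cause. The pneumonitis row requires evaluation and consultation, and 7.4.1 has the team discuss each patient weekly, so source records may well give the reason. What is missing is the AE dataset entry.
- *Not every Grade 1 event is lost.* Serious ones arrive through SAE reporting, and one that worsens enters at its higher grade.
- *The effect on results is limited.* Counts at Grade 2 and above stand. Section 10.3.3 specifies no any-grade incidence line, so a claim that such a figure is understated goes beyond the plan. Safety is not a primary or secondary objective, and no decision rule in section 10 uses AE counts.

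These points narrow the concern. None of them lets a site follow both 6.1 and 8.5.1, and none puts the Grade 1 hold events into the safety tables.

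**Conclusion.** The concern holds in a limited form. Sections 6.1 and 8.5.1 cannot both be followed for non-serious Grade 1 events. Following 6.1 would leave events that hold drug under 3.3 out of the AE dataset and out of tables that do not disclose the omission.

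The affected set is non-serious Grade 1 events that do not worsen. The part that matters most is pneumonitis and neurologic events, where Grade 1 triggers a hold. The number cannot be stated. The PFS6 decision rules are unaffected.

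The conclusion assumes that the 10.3.3 tables are built from AEs collected under 6.1. If sites have in practice been collecting Grade 1 events under 8.5.1, the data may be complete and only the text needs correcting; the documents do not say which rule has been applied. This should be corrected for the sake of the safety record, but it does not threaten the trial's main conclusion.

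**What to change.** Reconcile 6.1 with 8.5.1.

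1. At minimum, amend 6.1 so that any Grade 1 AE that is serious, or that leads to a hold or discontinuation of study drug under 3.3, is recorded in the AE database.
2. For the remaining Grade 1 AEs, either collect them or keep the exclusion. If it is kept, state the threshold in 8.5.1, check it against the supplier agreement, and label the 10.3.3 tables as Grade 2 and above plus the Grade 1 events in item 1.
3. Deal with patients already treated. Section 1.2.7 reports that 15 NHMP patients had been accrued by the interim analysis, so a new rule would give mixed ascertainment. Either abstract earlier Grade 1 hold events from source records, or report the tables by period of ascertainment.

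The cost is a short amendment, modest extra data entry, and either the retrospective abstraction or a split table. Full Grade 1 collection would cost more, and the minimum does not require it. The dose-hold rules in 3.3 are left as they are.
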